27. Process of Informed Consent. How will the process of informed consent be structured in order to be conducive to rational and thoughtful decision making by the subject/subject's legally authorized representative without any element of coercion or undue influence? *Note: Depending upon the nature of the study, the degree of risk, and the subject population, factors that should be considered in structuring the process of consent include: a) the environment and location where informed consent will be negotiated; b) the amount of time allotted to the process of informed consent; c) the involvement of non-investigators (e.g., technicians) who can help explain the research to the subject/representative; d) utilization of a delayed consent procedure where the subject/representative is encouraged to discuss participation in the study with family, friends, counselors, or other confidants before they sign the consent form; and e) utilization of a re-consent procedure at periodic intervals. This section should clearly document that appropriate attention will be given to the process of informed consent. If children/youth will be subjects, this section should separately address the process of informed assent that should be specifically designed for the age range of the subjects.*

For patients who appear eligible for the study following a "standard-care" examination, the study will be explained to the child's parent(s) or guardian. Parents or guardians who express an interest in the study will be given a copy of the consent form. Written informed consent will be obtained from the parent or guardian prior to performing any study-specific procedures, which are not part of the patient's routine care. All consent process will be in a private room. Parents and children will be given enough time to read consent and ask questions. If they want, they can take a copy of consent to home.

28. Subject/Representative Comprehension. How will it be determined that the subject/subject's authorized representative understood the information presented? *Note: All investigators have a legal and an ethical obligation to ensure that the prospective subject/representative has sufficient knowledge and comprehension of all of the elements of informed consent to enable them to make an informed and enlightened decision whether or not to participate or allow participation in research. The elements of informed consent include the purpose of the study, procedures, potential risks, potential benefits, alternatives, and any other information pertinent to informed consent. The fact that an individual is prepared to sign the informed consent form and has no unanswered questions does not necessarily represent sufficient evidence of an adequate level of comprehension. Some investigators, therefore, choose to determine the level of a person's comprehension by*

Efficacy of Intermittent Occlusion Therapy Glasses for Amblyopia-Dense, Deprivation and Myopic Anisometropia

Amblyopia

Approved 02/08/16

Amended: 05/12/16; 06/27/16; 06/29/16; 07/26/16, 09/13/16, 09/19/16, 09/27/16, 12/15/16, 01/26/17, 03/02/17, 06/20/17, 11/1/17, 12/19/17, 08/27/18, 12/18/18

questioning the individual concerning their understanding of all the elements of informed consent. This section should clearly document that the investigator has an adequate plan in place to assure existence of an acceptable level of comprehension of all the elements of consent.

If children/youth and/or incompetent adults will be subjects, this section should also include a specific plan to assess comprehension during assent.

As a part of the informed consent process, once the parent/guardian has read the informed consent form and decided to participate, the investigator will ask the parent/guardian a series of questions to assess the parent/guardian understanding of the study requirements, risks and benefits. Once the child has read the assent form, or the assent has been read to the child, and the child has decided to participate, the investigator will ask the child a series of question to assess the child's understanding of the study.

We have an assent form for children 7 years old, which uses very simple language to describe the study. They will be given enough time to ask questions.

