- Treatment is continued until there is no further improvement in amblyopic eye acuity (improvement defined as >1 line) between two consecutive 12-week visits, confirmed by a re-test. Once there is no improvement of one or more lines, the patient's participation in the study is over and treatment is at investigator's discretion.

Notes

1. The study will provide patches or IO-therapy glasses.
2. If a patient is noncompliant with treatment, the parents should be encouraged to persist with their efforts to treat to the best of their ability.
3. Prior to deviating from the treatment protocols or prescribing non-protocol treatment, the situation should be discussed with the PI.

Efficacy of Intermittent Occlusion Therapy Glasses for Amblyopia-Dense, Deprivation and Myopic Anisometropia

Amblyopia

Approved 02/08/16

Amended: 05/12/16; 06/27/16; 06/29/16; 07/26/16, 09/13/16, 09/19/16, 09/27/16, 12/15/16, 01/26/17, 03/02/17, 06/20/17, 11/1/17, 12/19/17, 08/27/18, 12/18/18

Randomization of Eligible Patients

1. Once a patient is randomized, the patient will be included in the analysis regardless of whether the assigned treatment is received or not. That is to adhere to “intent-to-treat” design. Thus, the investigator must not randomize a patient until he/she is convinced that the parent/guardian will accept and comply with either of the treatment regimens. Regardless of whether the patient receives the assigned treatment or not, the patient is still considered enrolled in the study and every effort should be made to perform the follow-up examinations according to the study protocol.
2. A patient is officially enrolled when the randomization process is completed.

Delay in Randomization

1. Visual acuity testing and the ocular motility examination must be performed no more than 7 days prior to randomization. If randomization is delayed beyond 7 days, then these tests must be repeated to confirm eligibility and establish the baseline measures for the study.
2. No other parts of the examination (including the refraction) need to be repeated if they were performed within 6 months prior to randomization.

Compliance

A calendar log will be maintained by all families. These logs will be reviewed at each of the protocol visits. The investigator's assessment of compliance will be recorded on the Follow-up Examination Form.

Follow-up Interactions

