After randomization, all patients (from both severe amblyopia and deprivation amblyopia groups) will have the following study visits/interactions:

Telephone Call

- Each patient will be contacted by the coordinator via telephone 4 weeks following the beginning of treatment to answer any questions and to encourage compliance with treatment.
- 12 ± 1 weeks after treatment begins : primary outcome visit

Primary Outcome Visit (occurs 12 ± 1 weeks after treatment begins)

Testing will include the following:

1. Visual acuity

Measured in each eye (worse eye first) by a certified examiner using the ATS single-surround HOTV acuity protocol.

2. Titmus fly and Randot Preschool Stereoacuity test

3. Ocular alignment assessed with the SPCT

4. Re-testing of visual acuity in the amblyopic eye (if indicated)

If amblyopic eye visual acuity has not improved from randomization by at least one line, then the acuity will be re-tested at this visit.

The results of the re-test will be used only to determine if the patient will continue study participation with the same study-mandated treatment. The first visual acuity will be used as the primary outcome visual acuity. If neither the test nor the re-test is one line better than the visual acuity at treatment, then study participation ends.

Efficacy of Intermittent Occlusion Therapy Glasses for Amblyopia-Dense, Deprivation and Myopic Anisometropia

Amblyopia

Approved 02/08/16

Amended: 05/12/16; 06/27/16; 06/29/16; 07/26/16, 09/13/16, 09/19/16, 09/27/16, 12/15/16, 01/26/17, 03/02/17, 06/20/17, 11/1/17, 12/19/17, 08/27/18, 12/18/18

Follow-Up Visits after the Primary Outcome Visit

For patients in either treatment group with at least one line of improvement in amblyopic eye acuity at the primary outcome examination, follow-up visits will occur every 12 ± 1 weeks until no improvement of one or more lines is seen.

At each post-primary outcome visit, visual acuity will be measured in each eye (worse eye first) by a certified examiner using the ATS single-surround HOTV acuity protocol. Acuity in the amblyopic eye will be re-tested during the visit if visual acuity has not improved from the last visit by at least one line.

Future treatment plans depend on each visual outcome in the amblyopic eye:

- If the patient's vision in the amblyopic eye is improved 1-2 lines, continue the study for another 12 weeks;
- If no improvement for one visit, continue the study for another 12 weeks;
- If no improvement for two visits, stop.

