Ocular alignment will be assessed at baseline and at 12 weeks after randomization. Development of new strabismus (no tropia at baseline and the presence of near and/or distance tropia at follow-up) or an increase from baseline ≥ 10 PD will be tabulated by treatment group. Similarly, disappearance of a heterotropia and a decrease in the angle of a preexisting strabismus by ≥ 10 PD will be tabulated.

Sample Size:

The sample size for this study was calculated based on a standard two-sided trial with a continuous outcome. The calculations assume 5% type I error with 80% power; the standard deviation of change from the baseline was 0.14, and the effective size difference was 0.12. Therefore, we anticipate that we will require 46 total subjects (i.e., 23 for each group).⁴ Because the IO therapy glasses are a novel device used to treat severe amblyopia, we are uncertain how many 3-8 year-old patients will drop out from the study. According to an average 15% dropout rate in previous amblyopia studies^{1, 6}, we overestimate the sample size to be 28 in each group to account for attrition.

12. **Drugs and Devices.** Does this study involve investigational drugs or devices (test articles) and/or FDA approved drugs/devices used for off-label purposes? If the study involves a test article, identify the drug/device, provide the IND or IDE number and identify the holder of the number. If the study involves drugs/devices used for off-label purposes, this should be stated. If the study does not involve any test articles or drugs/devices used for off-label purposes, this should be stated. *Note: Research involving investigational drugs must comply with the FDA IND Regulations (21 CFR 312) govern research with medical devices. The FDA IDE Regulations (21 CFR 812) govern research with medical devices. In some cases it may be in the best interest of the subject and the investigator for an IND/IDE to be submitted to FDA even when there is no legal requirement.*

Yes. We use IO-therapy glasses and thermosensor. We attach the medical device form of IO-therapy glasses and thermosensor. IO-therapy glasses are FDA approved.

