20. Risk/Benefit Relationship. What is the relative risk/benefit relationship of the research compared with the therapeutic alternatives? *Note: The IRB relies upon a reasonably detailed analysis of the relative risk/benefit relationship of the research versus that offered by the therapeutic alternatives that are available to the subject should they choose not to participate. The relationship of the anticipated benefits versus the potential risks of the research must be at least as favorable to the subject as that presented by alternate therapies that are considered standard treatment for the disease in question. This section should clearly document that the research offers the subject an acceptable risk/benefit relationship when compared with the therapeutic alternatives.*

Compare to benefit that we may find an effective treatment for amblyopia, risk associated with this study is minimum.

FINANCIAL OBLIGATIONS AND COMPENSATION (21-23)

Efficacy of Intermittent Occlusion Therapy Glasses for Amblyopia-Dense, Deprivation and Myopic Anisometropia

Amblyopia

Approved 02/08/16

Amended: 05/12/16; 06/27/16; 06/29/16; 07/26/16, 09/13/16, 09/19/16, 09/27/16, 12/15/16, 01/26/17, 03/02/17, 06/20/17, 11/1/17, 12/19/17, 08/27/18, 12/18/18

21. Financial Obligations of the Subject.

The eye patches and optical corrections for IO-therapy glasses will be provided by the study at no cost. IO-therapy glasses will be loaned to patients. The patient or his/her insurance company will be responsible for the costs of visits that would be needed whether they were in the study or not (standard care visits). The enrollment visit, if needed, is at no charge.

22. Research Versus Standard Treatment Costs. Are any financial obligations of the subject incurred or

increased as a result of procedures performed solely for research purposes? If so, provide additional detail.

Note: The financial obligations of the subject may be increased as a result of research participation by such factors as additional diagnostic/follow-up tests; longer hospitalization; and/or administration of drugs/agents that are more expensive than alternatives. This section should clarify the subject's financial obligations relative to their participation in the research.

The patient or his/her insurance company will be responsible for the costs of visits that would be needed whether they were in the study or not (standard care visits). Subjects will not pay extra money.

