23. Financial Compensation for Participation.

The parent/guardian of each patient will be compensated \$25 for each follow-up visit, and \$50 for the primary outcome visit. For patients remaining in follow-up after the 12-week visit, \$25 will be paid for each 12-week interval visit, up to an additional \$100 (4 exams). All payments will be made using ClinCard. Subject would not be paid for a 5th or 6th visit.

Testing	Visit Schedule	Time	Payment
Enrollment testing		30-60 mins	\$25
Primary Outcome Visit	12 weeks after treatment begins	30-60 mins	\$50
Follow-Up Visits after the Primary Outcome*	12 weeks	30-60 mins	\$25
	12 weeks	30-60 mins	\$25
	12 weeks	30-60 mins	\$25
	Continue visits every 12 weeks until no improvement	30-60 mins	N/A
Total			

*follow-up visits will occur every 12 weeks until no improvement of one or more lines is seen.

* Definition of primary outcome: the 12-week exam visit is the primary outcome visit. For the patching group, after they switch to IO-therapy glasses, the first 12-week exam with IO-therapy glasses is also treated as the primary outcome visit.

SUBJECT IDENTIFICATION, RECRUITMENT, AND CONSENT (24-31)

24. Method of Subject Identification and Recruitment. Does the principal or secondary investigator have ethical/professional access to the names of potential subjects? If not, how will these names be obtained? How will prospective subjects be contacted for recruitment into the study? Attach a copy of any planned advertisements/notices. *Note: The identification and recruitment of subjects must be ethically and legally acceptable and free of coercion. In addition, the recruitment procedure should be designed to facilitate equitable selection of subjects with particular attention paid to the recruitment of study participants of both genders and from different racial/ethnic groups.*

Efficacy of Intermittent Occlusion Therapy Glasses for Amblyopia-Dense, Deprivation and Myopic Anisometropia

Amblyopia

Approved 02/08/16

Amended: 05/12/16; 06/27/16; 06/29/16; 07/26/16, 09/13/16, 09/19/16, 09/27/16, 12/15/16, 01/26/17, 03/02/17, 06/20/17, 11/1/17, 12/19/17, 08/27/18, 12/18/18

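### The primary outcome visit is timed from the start of treatment but baseline from randomisation, with no limit on the gap and no date for a randomised child who never starts

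*Combined protocol and SAP*

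**What the plan says.** The protocol uses more than one time origin for the same visit.

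- **Start of treatment.** The Section 11 heading reads "Primary Outcome Visit (occurs 12 ± 1 weeks after treatment begins", the list above it says "12 ± 1 weeks after treatment begins : primary outcome visit", and the payment table in Section 23 says "12 weeks after treatment begins". The telephone call is likewise set at "4 weeks following the beginning of treatment".
- **Randomisation.** Alignment is one of the tests listed for the primary outcome visit, yet the Ocular Alignment paragraph says: "Ocular alignment will be assessed at baseline and at 12 weeks after randomization". The acuity re-test at that visit is triggered "If amblyopic eye visual acuity has not improved from randomization by at least one line".
- **No origin named.** The visit schedule table in Section 11 gives only 12 ± 1 weeks.

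Under Delay in Randomization, acuity must be no more than 7 days old at randomisation, or it is repeated to set the baseline. There is no matching rule for a delay after randomisation, and the schedule has no acuity test at treatment start. Even so, the continuation rule at the primary outcome visit refers to acuity at treatment.

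On the analysis population, Randomization of Eligible Patients, item 1, says: "Once a patient is randomized, the patient will be included in the analysis regardless of whether the assigned treatment is received or not". The same item asks for every effort to complete follow-up as the protocol lays down, whether or not treatment is received.

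**The concern.** In a randomised comparison both arms should be measured over the same interval from a common origin. Here baseline is tied to randomisation and the outcome to a later event. That event is not defined, has no time limit, and happens after the child's arm is known. If the average wait differs between arms, so does the time available for change from spectacle wear, repeat testing or growing older, and that change would be counted as a treatment difference.

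The second consequence is more direct. Intent-to-treat is meant to keep children who never take up their assigned treatment. Read literally, the visit rule gives them no date for the primary acuity measurement. Their outcomes could then be missing, or collected at times each site chooses for itself. If non-starting is related to arm, the loss is too.

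**Working it through.** **1. The plan's own figures.** Inputs from Sample Size in Section 11: difference 0.12, SD of change 0.14 (units not stated; logMAR assumed), two-sided 5%, power 80%, dropout 15%.

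- Normal approximation: n per arm = 2 × [0.14 × (1.960 + 0.842) / 0.12]² = 21.4, so 22.
- Two-sample t-test: 22.4, so 23 per arm and 46 in total, as stated.
- Dropout: 23 / 0.85 = 27.06, so 28 per arm, as stated.

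The time origin does not enter this calculation, so the sample size stands.

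**2. Elapsed time.** Let d be the weeks from randomisation to treatment start. The visit window is 11 to 13 weeks, and baseline acuity is 0 to 1 week before randomisation.

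| d (weeks) | Randomisation to visit (11+d to 13+d) | Baseline acuity to visit (11+d to 14+d) |
|---|---|---|
| 0 | 11 to 13 | 11 to 14 |
| 1 | 12 to 14 | 12 to 15 |
| 2 | 13 to 15 | 13 to 16 |
| 4 | 15 to 17 | 15 to 18 |

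The documents give no value for d and no upper limit. Timed from randomisation, the top row would apply to every child in both arms.

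**3. What a difference in delay could do.** Spurious difference = (difference in mean delay) × (background gain per week). Neither factor is in the documents. For illustration only, assume that one arm waits 0 to 4 weeks longer and that background gain is 0 to 0.01 logMAR per week.

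- Lower end: either factor zero gives 0.
- Middle: 2 × 0.005 = 0.01 logMAR. With 23 per arm and no true difference, the two-sided rejection rate moves from 5.0% to about 5.6%.
- Upper end: 4 × 0.01 = 0.04 logMAR, with a rejection rate of 15.8%. This needs both extremes at once, and 0.01 per week over 12 weeks would itself be 0.12, the whole design difference.

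The shift favours whichever arm waits longer.

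**4. The child who never starts.** For this child d is undefined, so the visit date (d + 12 weeks after randomisation) is undefined too. The Ocular Alignment paragraph supplies a date, but for alignment only. If 1, 2 or 3 such children in one arm had no outcome (22, 21 or 20 against 23), power would be 80%, 79% or 78%, against 81% with none. The loss of power is small; the harm is to the completeness of the intent-to-treat comparison.

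**The case against.** Timing from treatment start has a sound purpose: it gives both arms the same treated time, which is defensible in what Section 3 calls a pilot. Timing from randomisation has a matching cost. With delays of 1 to 4 weeks, nominal treated time at the visit would be 12 − 1 = 11 down to 12 − 4 = 8 weeks.

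The delay may also be trivial. A child must have had a cycloplegic refraction within 6 months and at least 4 weeks in optimal spectacles, so the prescription is known before randomisation. With no acuity test at treatment start, the authors may have regarded enrolment and treatment start as practically the same moment.

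A site could also work out a date for a non-starter. The follow-up section opens by saying that the visits follow randomisation, the schedule counts alongside an enrolment column, and enrolment is defined as completed randomisation. Investigators are told not to randomise until convinced that the family will accept either arm.

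Much of this stands. Equal treated time is a legitimate aim, and the cost of changing origin is real. But equal treated time does not remove unequal time from baseline unless acuity is measured again at treatment start, and that is not scheduled. A date that a site can infer is not a rule: the explicit wording points to treatment start, and sites may infer differently. The safeguard before randomisation makes non-starters fewer, but the same item expressly provides for them.

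**Conclusion.** The inconsistency is in the current text, and two conclusions hold. The interval from baseline to primary outcome is uncapped and could differ between arms. A randomised child who never starts has no date for the primary acuity visit under the stated rule; this second conclusion rests on no assumption.

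The size and direction of any bias are unknown. Three stronger readings are tempting, and the documents support none of them.

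- **That the glasses arm necessarily waits longer.** A reader might infer this from "The eye patches and optical corrections for IO-therapy glasses will be provided by the study at no cost". That is a statement about cost. It does not say that lenses are ordered after randomisation or that there is a wait, and nothing says how soon patches are handed over. A longer wait for the glasses is plausible, not shown.
- **That the bias is a definite share of the 0.12 design difference in favour of the glasses.** Any such share multiplies two assumed figures and is zero if either is zero.
- **That the 15% dropout includes children who never start.** It is an average attrition rate from previous studies, and nothing breaks it down.

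One further limit: the available text has no explicit primary efficacy analysis. That change is measured from the randomisation baseline is inferred from the re-test trigger, the baseline rule and the use of change from baseline in the sample size.

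**What to change.** For the randomised severe-amblyopia cohort:

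1. Reconcile the Primary Outcome Visit text, the Ocular Alignment paragraph and the Section 23 payment table to one origin for the intent-to-treat primary outcome visit: 12 ± 1 weeks after randomisation. Name that origin in the visit schedule table, which at present names none.
2. At the least, apply that date to any child who has not started treatment.
3. Record the date treatment starts and report the delay from randomisation to start by arm.
4. Run a sensitivity analysis on elapsed time from baseline and on treated time at the visit.
5. Reconcile the two reference points for acuity at the primary outcome visit (randomisation for the re-test, treatment for continuation), since only one baseline measurement is scheduled.

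The separate clock in Section 23 for patching children who switch to the glasses can stay, and the change need not touch the non-randomised cohorts.

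The cost is a wording change and one date field. The real downside is that a child whose glasses arrive late will have had less than 12 weeks of treatment at the visit, by the length of the delay; items 3 and 4 make that visible.
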